6.2 Secondary Endpoint

- Overall diagnostic accuracy (sensitivity, specificity, PPV, NPV) of AIR and SR for detecting erosions and/or ulcers;
- Small bowel reading time of AIR and SR;
- Miss rate of AIR and SR for detecting erosions and/or ulcers;
- Correlation between VCE findings and clinical data.

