At the site of patient's enrolment, investigators will perform VCE by evaluating the video in standard mode according to the recommendations of the European Society of Gastrointestinal Endoscopy, at 10 frames per second in the small intestine, and 20 frames per second in the esophagus, stomach, and colon. Reference points (first gastric image, first duodenal image, first cecal image) will be manually selected by the reader. The cleanliness level will be assessed as adequate (excellent/good) or inadequate (fair/poor) according to the qualitative scale of Brotz. Inflammatory lesions will be described using the Nomenclature and semantic descriptions defined by Leenhardt et al. in the International Delphi consensus (17), specifically modified for this study to ensure inter-observer agreement in the description of lesions (see **Figure 1**). Lesions will be reported specifying their time of appearance (h: min: s, timing of single frames). In case of multiple inflammatory lesions (>5 per tertile), time of appearance won't be specified and the reader will quantify the pathology burden for every tertile reported as 5-10 or >10 inflammatory lesions, specifying the predominant type of inflammatory lesion). At the end of the reading, readers will also calculate the Lewis score for each video. The Lewis score, used to score the known Crohn disease, split up the small bowel in three tertiles based on transit time, evaluating separately for each tertile the presence of villous edema, ulcerations, and stenosis. The assessment of these parameters is based on number, longitudinal extent and specific characteristics. The final score is the highest value among the

three tertiles (see **Figure 2** for details). A score between ≥ 135 and < 790 indicates mild inflammation; and a score of ≥ 790 signifies moderate-to-severe inflammation (18).

Investigators at the enrolment centre will anonymize the video which will be randomly reallocated to another centre for the second blind reading assisted by AI (i.e., the readers performing the capsule reading in AI mode will not be aware of the results of the first reading in standard mode). The same instructions specified earlier will be applied to the AI-assisted reading, except for the reading speed, limited to 2-5 frames per second.

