To note, the first reading will always be performed at the centre where the patient is enrolled (not randomized). This choice is made to ensure that patients receive the standard level of care at the centre and have full access to clinical history and medical documents for the physician who ultimately diagnoses the condition.

Comparison and Shared Review

An external researcher will compare the results of standard and AI-assisted readings from all the centres to assess the agreement of the observations reported by both readers. For videos containing less than 5 inflammatory lesions per tertile, the correspondence of reading will be evaluated comparing the type and the timing of the lesions. For videos with diffuse disease and multiple lesions, the correspondence of readings will be evaluated considering the number of lesions category (5-10 or >10 , classified for predominant type) reported in a specific tertile. In case of disagreement (for example, lesions missed by either reader in AIR or SR), an external expert reader (read more than 500 capsules) will review the discordant footage, blind to the source of the videos, open exclusively to the footage being reevaluated.

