8. ANALYSIS AND STATISTICAL METHODS

8.1 Statistical Plan

Descriptive statistics will be provided in terms of mean \pm standard deviation (SD) or median and interquartile range interval (IQR) for the continuous variables; and in terms of frequency and percentage (%) or rate for the categorical variables. Group comparisons will be assessed by Student t-test or non-

parametric Mann-Whitney test for continuous variables and Chi-squared test or test for proportion for categorical variables.

The accuracy performances will be evaluated by assessing diagnostic yield (DY), accuracy, sensitivity, specificity, positive predictive value (PPV) and negative predictive value (NPV). Comparison of these metrics will be evaluated by test for proportions for independent samples or by McNemar test for paired samples. Analyses will be performed in both per-patient and per-lesion setting.

Further analyses to assess the predictors of diagnostic performance will involve the application of univariable and multivariable logistic regression models.

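### Reading time is measured twice per video by different readers, with AI-assisted speed free within 2-5 fps, but the named tests allow for neither pairing nor reader, so its interval would be miscalibrated

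*Protocol*

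**What the plan says.** Protocol section 6.2 lists "Small bowel reading time of AIR and SR" as a secondary endpoint, and section 1 names shorter reading time as something the study sets out to show.

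Section 7 (Video Capsule Reading) sets the SR speed "at 10 frames per second in the small intestine". For AIR it states: "The same instructions specified earlier will be applied to the AI-assisted reading, except for the reading speed, limited to 2-5 frames per second". Nothing says who sets the speed within that range, or whether a reader keeps to one speed.

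The same section sends each anonymised video at random to another centre for AIR, while "the first reading will always be performed at the centre where the patient is enrolled (not randomized". The two readings of a video therefore come from different readers at different centres.

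Section 8.1 gives one rule for continuous variables: "Group comparisons will be assessed by Student t-test" or the non-"parametric Mann-Whitney test for continuous variables and Chi-squared test or test for proportion for categorical variables". The only mention of paired data concerns the accuracy metrics: "Comparison of these metrics will be evaluated by test for proportions for independent samples or by McNemar test for paired samples". No reader or centre term appears. The protocol does not give the number of centres or readers, the videos per reader, or the expected spread of reading times. It does not mention recording the reader or the AIR speed used.

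**The concern.** Two features of the design bear on the precision of the reading-time comparison, and the stated tests allow for neither.

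- **Pairing.** Both times come from the same video. A long or lesion-rich video tends to be slow in both modes, and an independent-samples test ignores that covariance. This pushes its standard error up.
- **Clustering by reader.** The same selected frames take 5/2 = 2.5 times as long at 2 fps as at 5 fps. If readers differ in the speed they use, all AIR times from one reader share that reader's pace. SR times from one enrolling centre may likewise share a pace. Because the two readings never share a reader, pace does not cancel in the within-video difference. This pushes the true standard error above the naive one, whether or not the test is paired.

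The two errors work in opposite directions for an independent-samples test. For a paired test only the second remains. At stake is the reported AIR/SR time ratio and its interval.

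**Working it through.** **The plan's own figure.** The protocol gives no SD, intraclass correlation (ICC) or reader count for reading time, so there is no reading-time figure to reproduce. The number of videos comes from section 8.2 (primary endpoint). With discordant cells 11.5% − 8% = 3.5% and 9% − 8% = 1.0%, margin 0.02, difference 0.025, one-sided alpha 0.05 and 80% power:

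- s1² = 0.045 − 0.025² = 0.0444, so s1 = 0.2107; restricted-likelihood null variance s0² = 0.0590, so s0 = 0.2428
- n = [(1.645 × 0.2428 + 0.842 × 0.2107) / 0.045]² = 164.2

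This reproduces the stated 164, which is used as N below.

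**Assumptions (none stated in the protocol).**

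- Each AIR reader keeps one speed, and readers' speeds are uniform on 2-5 fps.
- Viewing time is selected frames divided by speed.
- Videos are shared equally among K AIR readers, so m = 164/K videos each.
- The video-level SD of log(AIR time/SR time) is s = 0.3, 0.45 or 0.6.
- For the independent-samples test, the video-level SDs are equal in the two modes and the within-video correlation is r = 0.3 to 0.7.
- Clustering of SR times by centre is left out.

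**Between-reader spread.** For speed uniform on 2-5, the SD of log speed is τ = 0.259 (τ² = 0.0671).

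**Formulas** (true standard error divided by the one the test would use).

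- True variance of the mean log ratio: (s² + m τ²)/N
- Paired test that ignores readers uses (s² + τ²)/N, so factor = √[(s² + m τ²)/(s² + τ²)]. This is √[1 + (m − 1) × ICC] with ICC = τ²/(τ² + s²) = 0.43, 0.25, 0.16 for the three values of s.
- Independent-samples test uses [s²/(1 − r) + τ²]/N, so factor = √[(s² + m τ²)/(s²/(1 − r) + τ²)].

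**Worked extremes.**

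- Paired, K = 5, s = 0.3: (0.09 + 32.8 × 0.0671)/(0.09 + 0.0671) = 14.6; √ = 3.8
- Paired, K = 12, s = 0.6: (0.36 + 13.67 × 0.0671)/(0.36 + 0.0671) = 3.0; √ = 1.7
- Independent, K = 5, s = 0.3, r = 0.3: 2.292/(0.1286 + 0.0671) = 11.7; √ = 3.4
- Independent, K = 12, s = 0.6, r = 0.7: 1.277/(1.2 + 0.0671) = 1.0; √ = 1.0

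| AIR readers | Paired test | Independent-samples test |
|---|---|---|
| 5 | 2.4-3.8 | 1.4-3.4 |
| 8 | 2.0-3.1 | 1.2-2.7 |
| 12 | 1.7-2.5 | 1.0-2.3 |
| 20 | 1.5-2.0 | 0.8-1.8 |
| 30 | 1.3-1.7 | 0.8-1.5 |

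A factor below 1 means the interval is too wide. In simulation (4,000 runs per case), a nominal 95% paired interval that ignores readers covered 38-76% with 5-12 readers. A t-interval on AIR-reader means covered 93-95%.

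**If readers differ little.** With a coefficient of variation of only 0.05 in 1/speed between readers, a within-reader coefficient of 0.3-1.0 and 180 videos, the factor for the AIR mean is 1.0-1.5 for 4 to 30 readers.

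**Effect on the conclusion.** Section 1 cites an 89.3% mean reduction, so AIR takes 10.7% of SR time. If that held at 5 fps and every reader used 2 fps, AIR would take 10.7% × 2.5 = 26.8%, still a reduction of about 73%. With 89.3% as the estimate and the variances above, the reader-level 95% interval for the reduction is about 85% to 92% with 5 readers and 87% to 91% with 12.

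**The case against.** The strongest reply has four parts.

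1. **The mechanism is inferred.** The protocol limits the speed to a range. It does not say that each reader picks one speed and keeps it, or that each reads many videos. If readers vary speed by video, that spread is video-level variance, which an ordinary standard error already captures. This stands, and it is why no single inflation factor can be given.
2. **Pairing offsets clustering.** For the independent-samples test, the reading that section 8.1 most naturally bears, the ignored covariance works against the clustering. With many readers the interval may even be too wide. This stands, and the table shows it. It does not make the test right: the two errors cancel only by chance.
3. **The finding that AIR is faster survives.** A reduction near 89% leaves room for any of these factors. This stands. A reader might infer that the reduction could be produced by the speeds a few readers use. The protocol's figures do not support that, since the slowest permitted speed still leaves about 73%.
4. **Modelling detail belongs in a statistical analysis plan.** Reading time is one of four secondary endpoints and has no margin or power calculation, and a plan not seen here may handle it. This lowers the weight of the point. But section 8.1 does not leave the method open: it names tests that, as written, do not fit the design. Reader and speed also have to be captured at the time of reading, or a later plan may be unable to use them.

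A reader might also infer flatly that the error bars are 2 to 4 times too narrow. That range needs few readers and stable, well-spread speeds, none of which the protocol states.

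**Conclusion.** The point holds for the method and not for any fixed multiplier. The size of the miscalibration runs from slightly conservative to severe, depending on reader count, stability of each reader's speed, video-level spread and which form of the test is used. The 2-5 fps limit alone does not settle any of these. The direction is clear only for a paired test, which would understate the standard error whenever readers differ systematically in pace.

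What is affected is the estimated size of the time reduction and its interval, for a secondary endpoint. A separate check of the primary per-patient yield comparison, with assumed reader-by-mode SDs of 1-2 percentage points and 4-10 readers, gave one-sided error of 5.0-6.5% against the nominal 5%. The primary test is therefore little touched. The change is worth making because it is cheap and has to be in place before readings begin.

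**What to change.** - On the reading form, record reader identity for every reading and the speed used for every AIR reading.
- In section 8.1, replace the Student t/Mann-Whitney comparison for reading time with a mixed model on log small-bowel reading time: mode as fixed effect, video and reader-by-mode as random effects. If AIR readers are few, use a t-interval on AIR-reader means of the log ratio.
- Report the AIR/SR time ratio with that interval, overall and by AIR speed used.

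The cost is two form fields, a sentence in section 8.1 and possibly a wider interval. No extra patients, readers or readings are needed.

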 - **SmartScan:** Based on an AI algorithm developed and validated for reviewing capsule videos of the stomach and small intestine, it eliminates redundant images and identifies 16 different types of abnormalities found in the images.
 - **SmartView:** Allows the operator to quickly "navigate" through the entire video, showing only the images selected by SmartScan and highlighting the selected video portions on the timeline that can be viewed separately from the rest of the footage.
 - **SmartFinding:** Displays only the images selected by the operator, providing a description and characterization of the detected abnormalities.

VCE will be performed at each centre according to local regulations and requirements, and the study protocol will address the bowel preparation regimen as well as the reading methods and post-procedural analysis for each patient.

Pre-Procedural Patient Management

To achieve homogeneous results, a standard bowel preparation regimen will be adopted, involving the intake of Polyethylene glycol (PEG) in a split-dose manner, as recommended by ESGE guidelines (16).

The regimen includes:

- The day before VCE: the patient may have breakfast and consume a light meal until 3 PM, followed by fasting. At 7:00 PM, take dose 1 of the bowel preparation with a very low volume PEG solution (PlenVu, Norgine).

- The day of VCE: take dose 2 in the morning of the procedure so that it is completed 2 hours before capsule ingestion, fasting from liquids for 2 hours after ingestion, and fasting from solids for 4 hours after capsule ingestion. After this, the patient is allowed to drink clear liquids and have a light meal.

Post-Procedural Management

Patient follow-up will occur according to routine clinical practice, collecting any cases of retention or adverse events. Patients undergoing VCE will be instructed to check for the expulsion of the capsule and to report any relevant symptom that may suggest potential capsule retention. Patients who do not notice the expulsion of the capsule within 2 weeks of ingestion will undergo an abdominal X-ray to exclude capsule retention. Clinical and laboratory data of all patients enrolled will be collected at follow-up visits (at 6 and 12 months).

Video Capsule Reading

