8.2 Sample Size

Sample size calculation is assessed at per-patient analysis based on previous evidence by Xie et al 2022 (14) in which the detection rate of erosions and ulcers (common lesions in suspected Crohn disease) in AI-assisted reading was 11.5%, compared to 9% in standard reading (i.e. a difference of the two proportion around $D=2.5\%$). Considering a non-inferiority one side test for the difference between correlated proportions. with a non-inferiority margin $M= 0.02$, a type I error α of 0.05, a power $1-\beta$ of 80%, a difference of the two proportion $D=0.025$ and a plausible proportion of concordance on positive detection in both AIR and SR of 8%, the sample size needed to establish the non-inferiority of AI-reading with respect to Standard Reading is $N=164$ patients (i.e. 164 VCE). The size will be raised up to $N=180$ in order to take into account a potential dropout rate up to 10%. Details about the sample size computation can be found in Liu, J., et al. (19); and in PASS sample size software documentation at https://www.ncss.com/wp-content/themes/ncss/pdf/Procedures/PASS/Non-Inferiority_Tests_for_the_Difference_Between_Two_Correlated_Proportions.pdf).

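### Sensitivity, specificity, PPV, NPV and miss rate are promised in absolute terms for each reading, but only footage on which the two readings disagree is ever verified

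*Protocol*

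**What the plan says.** Section 6.2 lists as secondary endpoints "Overall diagnostic accuracy (sensitivity, specificity, PPV, NPV) of AIR and SR for detecting erosions and/or ulcers" and "Miss rate of AIR and SR for detecting erosions and/or ulcers". Section 8.1 repeats the accuracy metrics, plans them per patient and per lesion, and adds: "Comparison of these metrics will be evaluated by test for proportions", independent or paired.

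Section 7 describes how the readings are made and reconciled. The enrolling centre reads in standard mode. Investigators then "anonymize the video which will be randomly reallocated to another centre for the second blind reading", which is AI-assisted. An external researcher compares the two reports. Where they disagree, an expert "will review the discordant footage, blind to the source of the videos, open exclusively to the footage being reevaluated". No step re-reads footage on which the two readings agree, whether positive or negative.

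Section 7 also provides for follow-up at 6 and 12 months: "Clinical and laboratory data of all patients enrolled will be collected at follow-up visits". It is not linked to the accuracy endpoints.

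**The concern.** Each promised metric needs to know whether a lesion was truly present. The plan settles that only for discordant footage. Where both readings are negative the patient can only be counted as a true negative, and where both agree on a lesion it can only be counted as a true positive.

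A lesion missed by both readings therefore leaves the false negatives of both and enters their true negatives. A false call made by both enters the true positives. The resulting figures describe performance against the two readings combined, but they would be published as absolute accuracy. Section 8.1 also compares the metrics between readings, and part of that comparison inherits the problem.

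**Working it through.** **Inputs (Section 8.2, erosions and ulcers, per patient).** Detection rates are AIR 11.5% and SR 9%, with "a plausible proportion of concordance on positive detection in both AIR and SR of 8" per cent. Hence both positive a = 0.08, AIR only b = 0.115 − 0.08 = 0.035, SR only c = 0.09 − 0.08 = 0.01, both negative d = 0.875.

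**The plan's own figure.** These cells reproduce its sample size. With D = 0.025, M = 0.02, one-sided α = 0.05 and 80% power, the paired score test with restricted maximum-likelihood null variance has v1 = 0.045 − 0.025² = 0.044375 and v0 = 0.05896. Then n = (1.645√0.05896 + 0.842√0.044375)² / 0.045² = 164.2, against the stated 164. At that size about 0.875 × 164 = 143.5 videos are negative on both readings, so nothing from them reaches the expert.

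**Joint misses.** Assume that every discordant call is confirmed and that there are no shared false calls. Let j be the share of all patients with a lesion that both readings miss.

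- AIR sensitivity = 0.115/(0.125 + j); SR sensitivity = 0.09/(0.125 + j)
- Miss rate = 1 − sensitivity
- AIR NPV = 1 − (0.01 + j)/0.885; SR NPV = 1 − (0.035 + j)/0.91
- Sensitivity difference = 0.025/(0.125 + j); ratio = 0.115/0.09 = 1.278 for every j
- Odds ratio between misses = a·j/(b·c)

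Independent misses give j = 0.035 × 0.01/0.08 = 0.44%, or 0.72 of 164 patients. The 1% and 2% shares are assumptions.

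| j | Odds ratio | AIR sens. | SR sens. | Difference (points) | AIR miss rate | SR miss rate | AIR NPV | SR NPV |
|---|---|---|---|---|---|---|---|---|
| 0 (as reported) | – | 92.0% | 72.0% | 20.0 | 8% | 28% | 98.9% | 96.2% |
| 0.44% | 1.0 | 88.9% | 69.6% | 19.3 | 11% | 30% | 98.4% | 95.7% |
| 1% | 2.3 | 85.2% | 66.7% | 18.5 | 15% | 33% | 97.7% | 95.1% |
| 2% | 4.6 | 79.3% | 62.1% | 17.2 | 21% | 38% | 96.6% | 94.0% |

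**Against sampling error.** Expected positives are 0.125 × 164 = 20.5. The standard errors are √(0.92 × 0.08/20.5) = 6.0 points for AIR and √(0.72 × 0.28/20.5) = 9.9 points for SR. Under independence the bias is 3.1 points for AIR (about half a standard error) and 2.4 points for SR (about a quarter).

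**Shared false calls.** Let s be the share of patients falsely called positive by both (assumed, with j = 0). AIR PPV = 1 − s/0.115, SR PPV = 1 − s/0.09, and specificity = 1 − s/(0.875 + s); all are reported as 100%. At s = 0.5% they are 95.7%, 94.4% and 99.4%; at s = 2%, 82.6%, 77.8% and 97.8%. The sensitivity ratio becomes 0.110/0.085 = 1.29 and 0.095/0.070 = 1.36. The paired detection difference stays at 2.5 points, because s cancels.

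**When the expert errs.** Suppose half of the AIR-only calls are false but confirmed. The true AIR-only cell is 0.0175, and the independent joint-miss share is 0.0175 × 0.01/0.08 = 0.22%. SR is still reported at 72.0%, but its true value is 0.09/(0.08 + 0.0175 + 0.01 + 0.0022) = 82.1%. The direction reverses.

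**Stability of the independence estimate.** With 164 patients the chance of no SR-only patient is 0.99^164 = 0.19. The estimate b·c/a is then exactly 0, so in about one study in five it would suggest no joint misses at all. Over simulated studies its 5th to 95th percentile is 0% to 1.4% of patients.

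Per-lesion cells are not given, so per-lesion figures cannot be computed.

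**The case against.** The strongest defence is that the protocol names no reference standard, and that a statistical analysis plan, not shown here, could name one, choose the leading comparison and add a sensitivity analysis. That is true of the labels. It does not cure the design: no analysis plan can verify footage that the reading procedure leaves unread, and Section 6.2 already states the endpoints in absolute terms.

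A second defence is that the effect is small, since the only joint-miss share derivable from the protocol moves AIR sensitivity by about 3 points, within sampling error. This stands, and it limits the point. Larger shares need positively correlated misses. The shared recording makes correlation plausible, but different readers, centres and reading modes, and the blinding, work against a strong one.

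Follow-up is no substitute reference. It bears on the later diagnosis of Crohn's disease and cannot show whether an erosion or ulcer was on the video.

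A reader might infer more than the documents support:

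- That the non-inferiority result is compromised. Joint misses add nothing to either reading's detections, so the yield comparison is untouched.
- That sensitivity is always overstated. This needs an expert who rules correctly.
- That the safe exclusion of Crohn's disease described in Section 1 is put in doubt. The NPV there concerns the disease in the long term; the one in Section 6.2 concerns lesions on the video.
- That the bias is known to be large. The protocol gives no joint-miss share, and even the 8% both-positive cell is a planning value.

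**Conclusion.** The point holds for the secondary accuracy endpoints. Followed as written, and provided the expert rules correctly on discordant footage, the plan gives sensitivity and NPV that are too high and miss rates that are too low whenever joint misses exist, and PPV and specificity that are too high whenever shared false calls exist.

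At the planning cells the bias in sensitivity is about 3 points for AIR and 2 for SR under independence, and about 7 to 13 points for AIR and 5 to 10 for SR if 1% to 2% of patients are jointly missed. The second range rests on an assumption. The AIR–SR difference in sensitivity shrinks from 20.0 to between 19.3 and 17.2 points over the same shares.

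Joint misses leave the primary yield comparison, the paired detection difference and the sensitivity ratio unchanged; shared false calls do move the ratio. This is a matter of what the secondary figures can be called. It should be corrected, but it does not threaten the trial's main conclusion.

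**What to change.** Amend Sections 6.2 and 8.1 as follows.

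1. Name the reference: a lesion counts as present if both readings report it, or if the expert confirms it on discordant footage.
2. Report sensitivity, specificity, PPV, NPV and miss rate only as relative to this combined, expert-resolved reading.
3. Lead the secondary comparison with the paired AIR–SR difference in expert-resolved detections, together with the sensitivity ratio.
4. Add a sensitivity analysis over joint-miss shares, starting at the independence estimate from the observed cells and extending upwards, with the implied odds ratio between misses beside each share. The independence estimate should not stand alone, since it is 0 in about one study in five. In such a study a discordant cell is empty and the odds ratio is undefined, which should be stated.

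The cost is a wording amendment, to be shared with the ethics committee under Section 12. It needs no additional patients or readings. The downside is that the headline accuracy figures will carry a caveat.
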